7.3. Degree of significance and power of the clinical trial

The main analysis will be carried out using a one-tailed statistical test with a significance threshold α set at 5%. The clinical trial is designed to ensure 80% power for the main analysis test. Secondary analyses will be carried out using two-tailed statistical tests with a significance threshold α set at 5%.

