In addition, the difference in the 2-year efficacy rate between the 2 materials are to be calculated; its unilateral confidence interval of 95% will be provided and the lower limit is will be compared against the non-inferiority limit.

The main performance analysis will be carried out on the PP population, in accordance with the recommendations for non-inferiority studies. This will be complemented by an analysis of the mITT population to check the stability of the results.

7.7.5. Analysis of secondary performance criteria:

Efficacy rate at 6 months based on radiological and clinical criteria: Description and comparison, between the PA1704 arm and the BioRoot™ RCS arm, of the 6-month efficacy rate by Pearson's Chi-2 test or Fisher's exact test.

Efficacy rate at 12 months based on radiological and clinical criteria: Description and comparison, between the PA1704 arm and the BioRoot™ RCS arm, of the 12-month efficacy rate by Pearson's Chi-2 test or Fisher's exact test.

Quality of apical obturation at T0 (complete obturation, under-filling or over-filling): Description and comparison, between the PA1704 arm and the BioRoot™ RCS arm, of the proportions of apical obturation quality by Pearson's Chi-2 test or Fisher's exact test.

Density of root canal filling at T0, 6 months, 12 months, 24 months: Description and comparison at each time point, between the PA1704 arm and the BioRoot™ RCS arm, of the proportions of canals with an

obturation density deemed sufficient and the proportions of canals free of voids, by Pearson's Chi-2 tests or Fisher's exact tests.

Progress of material resorption over 24 months, in the event of over-filling at T0 (6 months, 12 months and 24 months): Description and comparison, between the PA1704 arm and the BioRoot™ RCS arm, of the proportions of patients with resorbed materials among patients who were over-filled at T0 by Pearson's Chi-2 test or Fisher's exact test.

Pre-operative and post-operative pain experienced by the patient (VAS 0-100 mm) at T0 (end of surgery), 12h, 24h, 48h, 72h and 7 days: For each time point, description and comparison of the pain, between the PA1704 arm and the BioRoot™ RCS arm, by a Student, Welch or Wilcoxon test. A figure representing average pain as a function of assessment times per arm will be provided. The causes of the pain will be described.

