Maximum pain in the first 7 days and time to onset of maximum pain: Description and comparison, between the PA1704 arm and the BioRoot™ RCS arm, of the maximum pain experienced during the 7 post-operative days and its time to onset by a Student, Welch or Wilcoxon test.

Intra-operative pain relief between T0 and D7: Description of painkiller classes, reasons for use, frequency of use and cumulative dose per patient over 7 days. Description and comparison, between the PA1704 arm and the BioRoot™ RCS arm, of the proportion of patients who used *oral* pain medication between T0 and D7 by Pearson's Chi-2 test or Fisher's exact test.

Description of the surgical technique: Description and comparison, between the PA1704 arm and the BioRoot™ RCS arm, of the type of anesthesia, the technique used to remove the old filling material (if root canal re-treatment only), the technique used to shape the canal, the type of disinfectant and rinse solutions used and irrigation techniques, the method of application of filling material and gutta-percha condensation, and the coronal restoration technique, by Pearson's Chi-squared test or Fisher's exact test. Intraoperative complications will be described where appropriate.

Operator comfort and satisfaction: Description and comparison, between the PA1704 arm and the BioRoot™ RCS arm, of operator comfort criteria. Satisfaction will be described at T0 and 2 years, and the proportions of satisfied operators will be compared.

For the performance criteria (efficacy rate, filling density, and material resorption) evaluated at 3.5 years and 5 years in the PA1704 arm: These criteria will only be described.

7.7.6. Safety/tolerance analysis:

The tolerance analysis will focus on the Tolerance population. Tolerance data is to be expressed as the number of adverse events (AEs) and the number of patients reporting at least one AE. Severity, cause (filling material or surgical technique) and the time of occurrence shall be described. The proportions of AEs and patients with AEs will be compared between the 2 groups. The proportions of patients who used an additional dental consultation for significant post-operative complication or pain will be described and compared, between the PA1704 arm and the BioRoot™ RCS arm, by Pearson's Chi-squared test or Fisher's exact test.

Defects in the devices will be described in the form of a list and proportions will be compared between the 2 groups.

7.7.7. Intermediate analyses:

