No interim analysis of the primary criterion is planned. The main analysis will only be carried out after the 2-year follow-up of all patients enrolled.

Two interim analyses of the secondary criteria have been planned. These will be carried out after 6 and 12 months' follow-up for all included patients.

The alpha risk will not be inflated, as the main criterion will not be analyzed in the interim analyses. Therefore, no alpha risk adjustment method is required. The final analysis will focus on the primary and secondary criteria.

For patients treated with the PA1704 ready-to-use filling material and who agree to be followed-up with for up to 5 years, a non-comparative descriptive analysis of secondary performance and safety criteria at 3.5 years and 5 years will be carried out at the end of their participation.

7.7.8. Criteria for stopping the clinical trial from a statistical point of view:

None. Interim analyses are only used to collect data on secondary criteria before the end of the study. The conclusion on the non-inferiority of PA1704 compared to BioRoot™ RCS will only be made on the final analysis at 2 years.

7.7.9. Changes to the statistical analysis plan:

The statistical analysis plan will be drawn up before the first interim analysis is carried out. The initial analysis strategy may undergo minor modifications following each data review, and the new statistical analysis plan will be described in detail at that time.

7.7.10. Specification of sub-groups for further analysis:

The following sub-group analyses will be carried out, at least on the PP population, during the final analysis at 2 years. Other factors not considered in this protocol may be added in the Statistical Analysis Plan.

- For the primary criterion, the rate of effective treatment at 2 years:
 - Prognostic factors at enrolment
 - Presence or absence of a periapical lesion,
 - Indication for endodontic treatment: initial versus repeat endodontic treatment,
 - Factors related to the surgical procedure
 - Type of rinse solution used to finalize root canal disinfection,
 - Operating techniques used: technical platform used (whether or not a microscope was used), manual files versus continuous rotation versus alternative rotation.
- Post-operative pain:
 - Operating techniques used: manual files versus continuous rotation versus alternative rotation.
 - Initial pulp pathology (pre-existing inflammatory situation or necrosis or live pulp),

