 - o Preoperative pain (symptomatic tooth at enrolment, preoperative VAS).

7.7.11. Handling missing, unused or erroneous data, including drop-outs and withdrawals:

No imputation method is planned. However, as stated above, patients with treatment failure at 6 or 12 months will be withdrawn from the study and will be considered to have treatment failure at 24 months.

7.7.12. Exclusion of certain information from the hypothesis tests, if relevant:

None.

7.7.13. In the case of multi-center investigations, minimum and maximum number of subjects to be included for each center:

Each center will include 22 to 24 patients with an indication for initial or repeat endodontic treatment. The number of repeat treatments may vary between centers, but will total 30% in the sample. Some investigators, because of their specialty in endodontics, will include a majority of patients with an indication for repeat treatment, whereas GP investigators will probably have more indications for first-line treatment.

8. Data management

Procedures for examining data, cleaning databases, issuing and resolving data queries:

See Chapter 6.6, Data quality and monitoring section.

Procedures for verification, validation and securing of the electronic clinical data systems, where applicable:

The data collected in electronic CRFs is recorded directly in an electronic database using ENNOV software and hosted on a secure health data server in accordance with current regulations. The data collected in the paper logbooks is entered by the CRO into the electronic database using ENNOV software.

Data retention:

See the Archiving section in Chapter 12.4.

9. Amendments to the clinical investigation plan

Requests for substantial modifications will be sent by the CRO, on behalf of the sponsor, to the relevant ethics committees for their opinion and to the competent authorities for authorization, in accordance with law 2004-806 of 9 August 2004 and its implementing decrees in force.

Similarly, non-substantial modifications will be sent for information.

An updated version of the amended protocol must be dated. This new version will be sent to the investigators.

The patient information leaflet should be amended if necessary.

10. Deviations from the clinical investigation plan

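### Post-operative pain is compared by unadjusted tests although pre-operative VAS and the ET/ER stratum are available, which costs precision without causing systematic bias

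*Combined protocol and SAP*

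**What the plan says.** Section 7.7.5 lists "Pre-operative and post-operative pain experienced by the patient (VAS 0-100 mm) at T0 (end of surgery), 12h, 24h, 48h, 72h and 7 days". At every assessment it plans a description and a "comparison of the pain, between the PA1704 arm and the BioRoot™ RCS arm, by a Student, Welch or Wilcoxon test". The same family of tests is applied to a comparison "of the maximum pain experienced during the 7 post-operative days and its time to onset by a Student, Welch or Wilcoxon test". Section 7.7.3 offers only two-sample tests and reserves the Wilcoxon test for samples below 30, so with about 80 per arm the comparison will in practice be of raw means. Section 7.3 sets secondary tests at two-sided 5%.

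Baseline pain and painkillers do appear elsewhere:

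- Pre-operative pain is itself described and compared between arms (Section 7.7.5).
- Section 7.7.10 lists "Preoperative pain (symptomatic tooth at enrolment, preoperative VAS") as a sub-group factor for post-operative pain, next to initial pulp pathology, and states: "The following sub-group analyses will be carried out, at least on the PP population, during the final analysis at 2 years".
- Section 7.7.5 plans a "Description of painkiller classes, reasons for use, frequency of use and cumulative dose per patient over 7 days" and a between-arm comparison "of the proportion of patients who used *oral* pain medication between T0 and D7 by Pearson's Chi-2 test or Fisher's exact test".
- Section 6.1 stratifies randomisation by ET versus ER.

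No part of Section 7.7 states a covariate-adjusted pain model, or says how VAS and painkiller results are to be read together.

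**The concern.** The population mixes irreversible pulpitis, necrotic pulp, living pulp and about 30% re-treatments, so starting pain is likely to vary widely. Section 7.7.10 itself treats pre-operative pain as relevant to post-operative pain. A sub-group analysis does not adjust the overall comparison, and a baseline comparison between arms can show an imbalance but not correct it. The pain test also ignores the factor on which randomisation was stratified.

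What is at stake is the sharpness of a secondary comparison in the first human use of PA1704. A wider interval makes it harder to say whether the ready-to-use form changes early pain.

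Painkillers raise a separate question of interpretation. Patients take them in response to pain after allocation, so each VAS score is pain after whatever relief the patient took. Frequency and cumulative dose are described but not compared between arms. Two non-significant results, one on VAS and one on the share of users, could then be reported as similar pain.

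**Working it through.** **1. The plan's own figure.** The only sample-size calculation is for the primary criterion (Section 7.2): 90% in both arms, margin 13 points, one-sided 5% (Section 7.2), 80% power (Section 7.3).

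n = (1.645 + 0.842)² × 2 × 0.90 × 0.10 / 0.13² = 65.9, so 66 per group. Then 66 × 1.20 = 79.2, so 80. Both stated figures reproduce. No SD, target difference or power is given for pain.

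**2. Inputs for pain.** 80 per arm and two-sided 5% come from the plan. The SD (20 to 30 mm) and the correlation r between pre-operative and post-operative VAS (0.3 to 0.5) are assumptions.

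**3. Unadjusted comparison, SD 25 mm.**

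- SE = 25 × √(2/80) = 3.95 mm.
- Detectable difference at 80% power = 3.95 × (1.96 + 0.84) = 11.1 mm.

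**4. Adjusted comparison.** Residual SD = SD × √(1 − r²).

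- r = 0.3: 11.1 × √0.91 = 10.6 mm.
- r = 0.5: 11.1 × √0.75 = 9.6 mm.

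The variance falls by r², that is 9% to 25%. This equals 1/(1 − r²) = 1.10 to 1.33 times as many patients.

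Detectable difference in mm, over a range of assumptions:

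| Per arm | SD (mm) | Unadjusted | r = 0.3 | r = 0.5 |
|---|---|---|---|---|
| 80 | 20 | 8.9 | 8.5 | 7.7 |
| 80 | 25 | 11.1 | 10.6 | 9.6 |
| 80 | 30 | 13.3 | 12.7 | 11.5 |
| 66 | 25 | 12.2 | 11.6 | 10.6 |

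At SD 25 mm and 80 per arm, power for a 10 mm difference is Φ(10/SE − 1.96): 72% unadjusted, 76% at r = 0.3 and 83% at r = 0.5.

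**5. Chance imbalance.** The between-arm difference in baseline mean has an SD of √(2/80) = 0.158 baseline SDs. An imbalance of that size shifts the unadjusted VAS difference by r × 0.158 × 25: about 1.2 mm at r = 0.3 and 2.0 mm at r = 0.5. The direction is random.

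**6. Planned test of painkiller use.** Power = Φ[(d − 1.96 × SE₀)/SE₁], with d the difference in shares, SE₀ pooled and SE₁ unpooled, 80 per arm and assumed shares.

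- 30% v 40%: (0.10 − 1.96 × 0.0754)/0.0750 = −0.64, power 26%.
- 30% v 50%: (0.20 − 1.96 × 0.0775)/0.0758 = 0.64, power 74%.
- 30% v 60%: (0.30 − 1.96 × 0.0787)/0.0750 = 1.94, power 97%.

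**The case against.** The strongest reply is that the plan neglects neither variable and that nothing here threatens its conclusion. Much of this stands.

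- **Bias.** With 1:1 randomisation, leaving out baseline VAS costs precision but gives no systematic error. It cannot by itself make a more painful sealer look equal.
- **Coverage.** Pre-operative pain is compared between arms and used as a sub-group factor. Painkiller use is described in detail and its share of users tested. Section 7.7.6 also compares additional consultations for complications or significant pain, another route by which pain could surface.
- **Status.** Pain sits among the secondary performance criteria, not in the tolerance analysis of Section 7.7.6. Its objective is worded as a description, and it does not enter the non-inferiority conclusion.
- **Legitimacy.** VAS with painkillers available is a valid treatment-policy comparison. It needs a label and a joint reading, not replacement.
- **Detail to come.** Section 7.7 leaves further detail to the Statistical Analysis Plan.

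A reader might infer that painkillers could make a more painful sealer show the same VAS. The documents do not support that. They give no relief per dose and no expected shares of users. If 50% versus 30% took painkillers and relief were 10 to 30 mm, the hidden part would be 0.20 × 10 to 0.20 × 30 = 2 to 6 mm. A true 10 mm difference would still show as 8 to 4 mm. Hiding a difference completely would need a true difference of 6 mm or less, below the 11.1 mm detectable in the first place.

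One caution bears on the fix. In Section 6.5.2, pre-operative pain is listed with the enrolment data ahead of randomisation, but the handover of the patient record that holds it is listed after treatment. Table 3 times the score at the start of each session, so some patients have two. No section says that the first score precedes knowledge of the allocation, and patients are not blinded.

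**Conclusion.** The point holds as one of precision and interpretation. The VAS tests in Section 7.7.5 leave out a baseline score the trial collects and the plan regards as relevant, and also the randomisation stratum. With SD 25 mm, 80 per arm and r between 0.3 and 0.5, the detectable difference would fall from about 11.1 mm to 10.6 to 9.6 mm. The size depends on r and the SD, neither of which the documents give, and no gain from the stratum is counted.

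The secondary point also holds, on assumed shares. The yes/no painkiller test would usually find a 30-point gap in users but often miss a 10-point gap, and no test covers the amount taken. It would go too far to call the pain comparison biased, or to treat it as a main safety test. The primary conclusion is unaffected.

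**What to change.** In Section 7.7.5, and in the Statistical Analysis Plan before any pain data are compared by arm:

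1. Compare VAS at each post-operative time point, and maximum 7-day VAS, by a linear model on arm, pre-operative VAS and ET/ER stratum. Report the adjusted difference with its 95% CI. The unadjusted tests can stay as a sensitivity analysis.
2. Define the covariate as the pre-operative VAS from the first session at V1, taken before the allocation is known. State in the visit procedure that it is recorded at that moment.
3. Label the VAS comparison as pain with painkillers available, and state that it is read together with painkiller use.
4. Add a between-arm comparison of cumulative dose or frequency of intake over 7 days. If dose is chosen, say how different painkiller classes are combined.

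The cost is wording in the protocol and analysis plan, with one line on the timing of the first VAS. No new patients, visits or data items are needed: the pre-operative score, the stratum and painkiller intake are already recorded.

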Delivery of MDs to centers: 2 BioRoot™ RCS kits and 15 PA1704 syringes will be delivered to each investigating center at the set-up visit; sachets containing additional caps, grip wings and endodontic tips will also be provided. Depending on the number of patients included, the number of canals to be filled, any device defects and the products' validity date, additional medical devices will be delivered to the investigating practices if necessary.

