By signing this protocol, the investigator and their collaborators undertake to keep confidential the identities of the subjects taking part in this clinical trial.

The observation booklet, the follow-up booklet and all other source documents attached to the CRF (including X-ray images) will be pseudonymized: each included patient will receive a four-digit identification code and a letter in the following format (NNN-CN). This alphanumeric code will be the only information to appear in the case report book and will enable the CRF to be linked to the patient *at a later date*.

NNN-CN

N: center number (from 1 to 7)

NN: center enrolment number (in chronological order of enrolment)

C: treatment arm: N = PA1704; R = BioRoot™ RCS

N: stratum number: 1 = Initial Endodontic Treatment (ET); 2 = Re-treatment (ER).

Examples:

Code of 1st patient enrolled at center 4 with indication of ET and treated with PA1704: 401-N1

Code of 12th patient enrolled at center 2 with indication of ER and treated with BioRoot™ RCS = 212-R2

The list of matching identification numbers and patient identities will be managed and kept by the investigator in paper format and archived with the trial documents specific to his/her center **only** at his/her premises.

Encoding of adverse events and device defects:

The IMDRF terminology (appendices A to G) will be used to encode adverse events related to medical devices and device defects (see details in chapter 14 on vigilance).

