7.7. Statistical methods

The statistical methods are based on the following elements and will be detailed in the Statistical Analysis Plan.

7.7.1. Sample description:

The description of the subjects enrolled who completed the trial and those enrolled who left prematurely will be presented using a table of absolute (N) and relative (%) frequency. Reasons for premature discharge and deviations from the protocol will be listed.

7.7.2. Descriptive analyses:

Clinical data collected at enrolment and at each visit will be described. Descriptive statistics will be presented according to the nature of the criterion analyzed:

- Quantitative variable: sample size, number of missing data sets, mean, standard deviation, median, minimum and maximum;
- Qualitative variable: absolute frequencies (N) and relative frequencies (%) per class in each group, number of missing data.

Graphs will be provided for each variable.

7.7.3. Comparative analyses:

A comparison of 2 independent means will be made using the Student's t-test; if the variances are unequal (verified by the Fisher's test), use the Welch's test instead of the Student's test. If the conditions for applying the Student test are not met (n < 30), the non-parametric Wilcoxon test is used.

2 independent percentages are compared using Pearson's Chi-2 test. If the conditions for application are not met (at least one theoretical number < 5), Fisher's exact test is used.

7.7.4. Analysis of primary performance criterion:

As a reminder, the primary performance criterion is the efficacy rate at 24 months of treatment based on clinical criteria assessed by the investigator (tooth functionality and pain level) AND radiological criteria assessed blind by independent reviewers (complete healing, reduction of lesions, failure). In the event of failure at 6 or 12 months, the patient will be considered to have failed at 24 months.

The primary criterion will be analyzed using 2 approaches, in accordance with the literature:

- **Primary analysis of soft criteria**: treatment rates with complete or incomplete cure are compared against failure rates;
- **Secondary analysis of strict criteria**: treatment rates with complete healing are compared against rates of failure or incomplete healing (complete healing can take up to 4 or 5 years).

The comparison of efficacy rates between the 2 groups will be carried out using the Dunnett and Gent χ^2 test (Dunnett CW and Gent M 1977; Elie C et al 2008).

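### Operator comfort and satisfaction: no test is named, and the plan's only tests assume independent samples although the same operators rate both sealers

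*Combined protocol and SAP*

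**What the plan says.** Section 7.7.5 plans a "Description and comparison, between the PA1704 arm and the BioRoot™ RCS arm, of operator comfort criteria", and continues: "Satisfaction will be described at T0 and 2 years, and the proportions of satisfied operators will be compared". Neither sentence names a test, although most neighbouring items do.

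The general rules are in 7.7.3 and in the synopsis under Statistical Methods. For proportions: "2 independent percentages are compared using Pearson's Chi-2 test". The fallback is: "If the conditions for application are not met (at least one theoretical number < 5), Fisher's exact test is used". Means are compared by Student, Welch or Wilcoxon tests, again for two independent groups. Section 7.3 makes secondary tests two-sided at 5%. No paired, clustered or operator-adjusted method appears. Section 7.7 opens by deferring detail: "The statistical methods are based on the following elements and will be detailed in the Statistical Analysis Plan".

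The data structure comes from other sections:

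- **Raters.** Table 3 (6.1) has the investigator rate comfort and satisfaction at T0 in the CRF, and again in an overall questionnaire at the end of the trial. The items include the pros and cons of one presentation against the other.
- **Centres.** The centre digit of the patient code runs from 1 to 7 (6.6.4), and each centre enrols 22 to 24 patients (7.7.13).
- **Devices.** Both sealers go to every centre (6.2): "2 BioRoot™ RCS kits and 15 PA1704 syringes will be delivered to each investigating center at the set-up visit".
- **Randomisation.** Patients are randomised 1:1, stratified by initial treatment or retreatment and not by centre or operator (6.1).

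**The concern.** An operator does not belong to an arm. The same few people use and rate both products, so a proportion of satisfied operators for PA1704 and one for BioRoot RCS come from the same individuals. Tests for two independent samples ignore that link. At procedure level, many ratings come from each operator, and an operator who prefers one device will tend to repeat that preference.

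At stake is a stated secondary objective (5.1). Section 4.1 describes the benefit expected for dental surgeons as practical, because the cement is ready to use. A comparison reported as significant could be read as support for ease of use.

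**Working it through.** The plan states no sample size, power or expected rate for operator satisfaction, so there is no figure of its own to reproduce. The number of operators is not stated either. One operator per centre (7) is assumed below, with larger numbers as a check. The planned 160 patients over 7 centres give 160/7 ≈ 23 procedures per centre, or about 11 per arm.

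**1. Ratings counted per operator.** With 7 operators rating each sealer, the smaller expected count is at most 7/2 = 3.5, so the plan's rule always selects Fisher's exact test. The paired alternative is the exact McNemar test, which uses only operators satisfied with one sealer and not the other.

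- *Five satisfied only with PA1704, two with both (7/7 v 2/7).* Fisher: 2 × C(7,5)/C(14,5) = 2 × 21/2002 = 0.021. Paired exact: 2 × (1/2)^5 = 0.0625.
- *Six satisfied only with PA1704, one only with BioRoot RCS (6/7 v 1/7).* Fisher: 2 × (49 + 1)/3432 = 0.029. Paired exact: 2 × (7 + 1)/128 = 0.125.
- *Three satisfied only with PA1704, four with both (7/7 v 4/7).* Fisher: 2 × C(7,3)/C(14,3) = 2 × 35/364 = 0.19. Paired exact: 2 × (1/2)^3 = 0.25. The conclusion is the same.

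The table gives simulated null rejection rates of the plan's Pearson/Fisher rule at a nominal 5% (30,000 runs per setting, 50% or 70% satisfied), by the correlation between an operator's two ratings.

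| Operators | +0.5 | 0 | −0.3 to −0.5 |
|---|---|---|---|
| 7 | 0.03–0.05% | 0.6–1.3% | 1.8–4.5% |
| 14 | 0.2–0.3% | 2.5–3.4% | 4.7–8.8% |
| 21 | 0.5–0.6% | 4.4–5.4% | 9.4–10.1% |

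So the rule is far too conservative when an operator's two ratings agree, and it can exceed 5% when they oppose each other and there are 14 or more operators. With 7 operators the long-run rate stayed below 5% in every setting tried, although individual p-values can still fall well below the paired ones, as shown above.

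**2. Procedure-level T0 ratings.** The model is logit(satisfied) = 1.4 + operator effect (SD 1) ± half of a mean-zero operator-by-device effect. The value 1.4 corresponds to about 80% satisfied, and there is no average preference. Each setting has 20,000 trials, with a pooled two-sided test at 5%.

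| Operator-by-device SD (logit) | 7 operators, 11 per arm each | 14 operators, 6 per arm each |
|---|---|---|
| 1 | 13% | 8% |
| 1.5 | 22% | 14% |
| 2 | 30% | 20% |

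With SD 0 and 7 operators, the pooled test rejects in 3.7%. Letting the 1:1 split vary at random within 7 operators of 23 patients each, and varying satisfaction from 50% to 85%, gives 4.9–5.7% when operators differ only in leniency and 13–34% with preference SD 1–2. A t-test on the per-operator differences stays at about 5% throughout.

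**The case against.** The strongest reply is that no faulty test has been specified. Section 7.7.5 names none for this item, the rule in 7.7.3 is worded for independent percentages and so does not by its own terms cover paired ratings, and detail is left to the SAP. The number of operators is not given. The documents do not say whether the end-of-trial questionnaire scores each sealer separately, or whether the contrast is sealer against sealer or T0 against 2 years. Randomisation of patients keeps the procedure-level test near 5% when operators differ only in leniency, and the larger rates rest on an assumed spread of device preference. Section 5.3 does not list ease of use among the claims to be verified.

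Most of this stands. A reader might infer that the plan prescribes Pearson or Fisher here and that its p-values are therefore wrong, or falsely significant. The documents do not support that: the test is only the default, the error has no fixed direction, and sharing operators does not by itself inflate procedure-level error. Nor do they support reading the 7/7 v 4/7 split as highly significant. That would require treating seven operators as about 77 ratings per arm, each operator repeating the same answer.

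What the reply does not remove is that the synopsis offers the independent-sample tests as the general rule for secondary criteria, that comfort is explicitly compared by arm, and that no alternative is given. Either possible contrast involves the same operators.

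**Conclusion.** The point holds as a minor one. The unit, the contrast and the test for operator satisfaction are unspecified, and the only tests on offer do not suit ratings given by the same operators on both sealers. For operator-level ratings the mismatch can make a p-value too small (0.021 against 0.0625) or the test very conservative. For procedure-level T0 ratings, the null rejection rate is near or below 5% without differing device preferences. With them it is about 13–30% with 7 operators and about 8–20% with 14.

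These sizes rest on assumed operator numbers and on logit SDs of 1 to 2 that no document supports or excludes. They also treat the operators as a sample from a wider population of users. The primary non-inferiority conclusion is not affected.

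**What to change.** In 7.7.5 and the SAP:

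- State the unit of analysis (operator or procedure) and the contrast (sealer against sealer, or T0 against 2 years).
- Analyse T0 ratings within operator, either as per-operator differences between sealers or with a model that includes operator and operator-by-device effects.
- If the end-of-trial questionnaire scores each sealer, analyse those scores as pairs by exact McNemar or sign test, with counts preferring each sealer. Otherwise report them descriptively without p-values.

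The change is wording only and needs no new data. The price is wider intervals and less impressive p-values on a secondary criterion.
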